9.5. Patient Disposition

At the end of the study, patient disposition will be presented in terms of:

- Number of patients screened
- Number of patients who fled an area of armed conflict and for whom no post-treatment data are available
- Number of patients not included in the study because they did not fulfil the eligibility criteria, and reason for non-inclusion
- > Number of patients randomised, total and by treatment group
- Number of randomised patients who received at least one dose of study treatment (ITT patients), total and by treatment group
- Number of randomised patients who completed the treatment period and who received all protocol-planned doses (treatment completers), total and by treatment group

- Number of randomised patients who received at least one dose of study treatment, except those who died due to causes clearly unrelated to the efficacy or safety of treatment (evaluable patients), total and by treatment group
- Number of randomised patients with no major protocol violations (per protocol patients), total and by treatment group
- Number of randomised patients who attended the following visits: screening visit, baseline assessment, visits during treatment period (D1 to D10), EOT visit, PK sampling visit, EOH visit, and follow-up visits at 3, 6, 12, 18 and 24 months, total and by treatment group
- Number of randomised patients who were withdrawn from the study, classified by reason for withdrawal, total and by treatment group
- Number of randomised patients with at least one protocol violation, classified by nature of violation (minor or major), total and by treatment group

Patient disposition will take into account the method of imputing missing data (see Section 9.2 Handling of Missing Outcomes and Patients Lost to Follow-up; p 58).

9.6. Demographic and Baseline Data

Descriptive summary statistics (n, mean, standard deviation, median, minimum, maximum) or frequencies and percentages will be presented for the following baseline characteristics of the study population:

- Demographic data
- Medical history
- Physical examination
- Vital signs
- Urine pregnancy test (only for women of child-bearing potential)
- Laboratory assessments
- ≻ ECG
- Karnofsky Performance Score
- Neurological examination
- Concomitant medication

9.7. Treatment Compliance

The dosing regimen of the study treatments, i.e. the IP and reference treatment, are fully described in Section 5 Treatments (p **Error! Bookmark not defined.**).

Treatment compliance will be analysed by describing, by treatment group, the number and percentage of patients who completed the treatment period. Patients in whom the treatment period was extended by one day (missed dose made up for at end of treatment) will be considered as having completed the treatment period. For patients who prematurely discontinued treatment, the duration of exposure will be presented.

9.8. Efficacy Analysis

9.8.1. Primary Efficacy Analysis

Primary Efficacy Endpoint

The primary efficacy endpoint is the outcome at 18 months. Outcome will be considered as a success if there is no evidence of trypanosomes in any bodily fluid and if the CSF WBC is $\leq 20/\mu$ L. Death and use of rescue treatment will be considered as a relapse, i.e. a failure. A patient who attends the 18-month visit or who is found again after an active search, who refused to undergo lumbar puncture but who has no signs or symptoms of HAT, and for whom the outcome was assessed as favourable at the latest assessment will be considered as a probable cure, i.e. a success, unless signs of relapse are detected on any assessment up to 24 months.

Primary Assessment Criterion

The primary assessment criterion is the success rate at 18 months.

Primary Test

The primary test is the Blackwelder non-inferiority test, based on the difference in the success rates and a margin of 13% (see Margin for "Acceptable Difference"; p 63).

Primary Measure of Size of Effect

The size of the treatment effect will be measured by the excess rate of success. The excess success rate is equal to the difference in the success rates between the two groups: size of effect = p_{fexi} - p_{NECT} . A negative success rate corresponds to a treatment effect in favour of NECT.

Margin for "Acceptable Difference"

The margin for an "acceptable difference" is set at $13\%^6$.

⁶ A survey was carried out by e-mail in the small population of local and international physicians who are experienced in treating patients with HAT, in order to assess the limit of an acceptable difference and the limit of an unacceptable difference in efficacy between an oral drug and NECT. Between the two limits, there is an "uncertainty zone". The median response for an unacceptable difference was 17% and the median response for an acceptable difference was 9%. A margin of 13% was chosen and is equal to the first tertile of the distribution of an unacceptable difference. It means that the unacceptable limit was above 13% for 2/3 of respondents, i.e. for 6/19 respondents, the unacceptable limit was below 13% and, for 12/19, the limit was above 13%. The margin of 13% is also at the mid-point between the median of an acceptable difference (9%) according to respondents and the median of an unacceptable difference (17%) for the same respondents (see results of the survey in Figure 4; p 108).

In life-threatening diseases, any margin of difference is clinically and ethically relevant, even if there may be differences in efficacy between treatments that are more or less interchangeable.

The observed absolute mean difference in the rate of favourable outcomes between the estimated treatment effects in various programmes/clinical studies is 17%. This would explain why a margin of 15% was used in a phase-III study on the efficacy of pafuramidine maleate (**Error! Reference source not found.**). B ecause products are not necessarily interchangeable, and efficacy is largely dependent on the project or programme, the margin of non-inferiority is not based on the limit of a non-pertinent difference, but rather on a difference in efficacy that is acceptable for an easily administered oral drug that can be used to treat HAT in primary healthcare facilities in outlying areas with little or no healthcare infrastructure (see Figure 4; p 107).

If the non-inferiority test is significant, this will not mean that fexinidazole is equivalent or superior to NECT, but rather that the practical advantage of an oral treatment counterbalances or outweighs a potential difference in efficacy in favour of NECT for the majority of experienced physicians. Interpretation of the size of the effect as concerns NECT and of the 95% confidence interval will prevail over interpretation of the test result in assessing the benefit-to-risk balance.

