9.1. Sample Size Determination

The calculation of the sample size has been revised. The total size of the sample is now calculated to be 390 patients, instead of 510, with the same 2:1 allocation ratio, i.e. 260 patients in the fexinidazole group and 130 patients in the NECT group. If the expected success rates are 94% with NECT and 89% with fexinidazole³ then the power of the final analysis is 80% with an acceptability ("non-inferiority") margin of 13%. The calculations were made for a one-sided type-1 error of 0.025.

No provision will be made for patients lost to follow-up since the missing outcome will be imputed, except for patients in areas of armed conflict (see Section 8.3).

³ The observed response rate for NECT was as high as 0.97 in the per protocol population and 0.965 in the ITT population (43). However, the definition of success was not the same as in this protocol, and the success rate for NECT would have been 0.95 or 0.94 if the same definition had been used. If fexinidazole has the same true success rate as NECT, and is equal to 0.95 or 0.94, then the power of the study will be greater than 99%. However, NECT is a co-administration of two drugs and there is no reason to expect fexinidazole to be more effective than effornithine alone. Available data show that the success rate with effornithine depends on the project and ranges between 0.89 and 0.90. If the expectations are 0.90 for fexinidazole and 0.95 for NECT, the exact power of the final primary analysis is 91.6%.

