This threshold is slightly lower than the historical difference between effornithine and melarsoprol at 12 months, i.e. \approx 15%. It should be noted that, at this stage, the study will be stopped if the result is significantly worse than the margin of an unacceptable difference, whereas the final analysis will be positive if the result is significantly better than the margin of an unacceptable difference.

Interim Analysis for Success

An interim primary analysis for success will be performed on the first 195 randomised patients who have theoretically reached 12 months of follow-up, excluding patients for whom no post-treatment data are available because the patient is known to have fled the area strictly for reasons of armed conflict. The analysis will be identical to the final primary analysis with the exception of the threshold for significance (see Adjustment of Type-I Error for Multiplicity) and the assessment visit, which will be 12 months instead of 18 months.

A sensitivity analysis, including all randomised patients, will be performed and will consider all patients who fled for reasons of armed conflict as failures.

If the interim primary analysis for success should not prove to be significant, no further interim secondary or sensitivity analyses will be performed. If the analysis proves to be significant, all of the interim secondary and sensitivity analyses will be performed in accordance with the approach described for the final analyses, i.e. those initially planned. In addition, the success rate at 18 months will be compared, using a superiority test, to the historical success rate for melarsoprol at 18 months, i.e. 73.7%. No adjustment of the threshold for significance will be made in this analysis. The time course of the success rate, i.e. EOT, 6 months, 12 months and 18 months, will be studied using the Kaplan-Meier approach. The cumulative failure rate at each visit will be presented graphically including historical data for melarsoprol and effornithine.

Adjustment of Type-1 Error for Multiplicity

No adjustment will be made for the FAs, because the study cannot be prematurely discontinued for success based on an FA. In this case, Chen has shown that performing such analyses slightly reduces the final type-I error (9).

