An adjustment of the type-I error will be made in view of the interim analysis for success. The Pocock approach will be used to determine the threshold of significance of the interim analysis as well as that of the final analysis. As a reminder, the final analysis will be performed on the planned number of patients.

10. Independent Steering Committee/Data Safety Monitoring Board

An Independent Steering Committee (ISC or DSMB) composed of at least 3 members independent of the Investigators and the Sponsor, will be set up prior to study initiation. The ISC will monitor the study in order to minimise any risk of harm to the patients included in the study. At predetermined intervals, the ISC will analyse safety data and all information related to SAEs or AEs leading to treatment discontinuation, and will put forward recommendations regarding the study if the benefit-to-risk balance for patients seems to be in jeopardy. The data and the intervals for review will be decided before, or soon after study initiation and documented in the ISC Charter.

The results of FAs will be presented to the ISC, who will decide whether or not the study can continue and whether the enrolment period should be extended.

The organisation of the ISC will be described in the ISC Charter, which will be prepared and approved prior to the first planned FA.

Additional *ad hoc* members may be invited to join the ISC if any safety concerns emerge, in order to give additional support to the competencies already present.

11. Quality Assurance and Quality Control Procedures

The Investigator must maintain appropriate accurate records to ensure that all aspects of conducting the study are fully documented, and that study data can be verified at the end of the study. These documents include the Investigator Site File, the patients' clinical source documents, screening/enrolment logs and other study-specific forms.

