Appendix 5 - Figures

Figure 3 – Statistical Power of the Study

Power of the study depending on the actual difference between the success rates and assuming a success rate of 94% for NECT

The power is improved if the efficacy of NECT is greater than 94%.

The power refers to the probability that the 95% confidence interval of the difference in success rates will exclude the margin of the chosen limit of an unacceptable difference.

The interval between an acceptable difference and an unacceptable difference, as reported by those who responded to the survey, is a "grey area" or a zone of uncertainty.

The Sponsor objective is to have at least an 80% chance of being significant if the actual difference is 5% in favour of NECT, and a very limited chance (1.45% = exact power = exact one-sided type-I error) of being significant if the actual difference is 13%.

Figure 4 – Acceptable and Unacceptable Limits of the Difference in Efficacy at the Testof-Cure Visit

Responses to two questions:

- what is the acceptable margin of difference in efficacy between an oral drug and NECT?
- what is the unacceptable margin of difference in efficacy between the two treatments?

[figure not shown]

Figure 5 – Failure Rate at each Timepoint by Compound

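### The final non-inferiority analysis has two significance levels: Pocock-adjusted in 9.11, but one-sided 0.025 with a 95% confidence interval in 9.1 and Figure 3

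*Protocol*

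**What the plan says.** Four places in the protocol bear on the significance level of the final primary analysis.

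- **Section 9.11, type-1 error adjustment:** "The Pocock approach will be used to determine the threshold of significance of the interim analysis as well as that of the final analysis". No number is given. The interim look is described as follows: "An interim primary analysis for success will be performed on the first 195 randomised patients", against 390 at the end. The same section says of the interim: "The analysis will be identical to the final primary analysis with the exception of the threshold for significance", the other stated difference there being the visit.
- **Section 9.1:** the power statement starts from assumed rates: "If the expected success rates are 94% with NECT and 89% with fexinidazole". For 260 plus 130 patients and a 13% margin, its conclusion reads "then the power of the final analysis is 80" per cent. On the error level it says: "The calculations were made for a one-sided type-1 error of 0.025".
- **Appendix 5, text to Figure 3:** power is defined as the chance of this event: "the 95% confidence interval of the difference in success rates will exclude the margin of the chosen limit of an unacceptable difference". Further down, the sponsor's aim is worded as an 80% chance of being significant at a true 5-point deficit.
- **Section 9.8.1:** the primary test is the Blackwelder non-inferiority test with a 13% margin. The closing sentence on the margin says that interpretation of the effect size and "of the 95% confidence interval will prevail over interpretation of the test result in assessing the benefit-to-risk balance".

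**The concern.** A two-look Pocock design splits the type I error between the looks, so the final test must be stricter than one-sided 0.025. A 95% interval that excludes the margin is a one-sided 0.025 test. The protocol therefore describes the same final comparison at two levels. It plans the power, and defines significance in Figure 3, at the less strict level.

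Two things are at stake. A final result in the gap between the levels would be significant by the Figure 3 text and not significant by 9.11, and the interval reported beside it would seem to contradict the test. Also, the 80% power belongs to a test that 9.11 says will not be used. The level matters because the interim look is a real chance to claim success: 9.11 says its purpose is to speed up the registration dossier.

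**Working it through.** **Inputs.** From 9.1: NECT 0.94, fexinidazole 0.89, margin 0.13, 130 and 260 patients, one-sided 0.025. From 9.11: looks at 195 and 390 patients, Pocock. The protocol gives no Pocock number, so I assume two looks at information fractions 0.5 and 1, an overall one-sided error of 0.025, and the 12-month and 18-month outcomes treated as one process (correlation √0.5 = 0.707).

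**1. Reproduce the stated power.** With unpooled variance:

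- SE = √(0.94×0.06/130 + 0.89×0.11/260) = 0.02847
- (0.13 − 0.05)/SE = 2.810
- Power at one-sided 0.025 = Φ(2.810 − 1.960) = Φ(0.850) = 80.2%

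This matches the stated 80%. The sample-size formula at 0.025 also returns 130 NECT patients, so planning used the unadjusted level.

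**2. Pocock level.** Solve 1 − P(Z₁ < c, Z₂ < c) = 0.025 at correlation 0.707. This gives c = 2.178, one-sided 0.0147, equivalent to a 97.06% two-sided interval. With equally spaced looks the same constant applies at both.

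**3. Power of the final test at that level.** Φ(2.810 − 2.178) = Φ(0.632) = 73.6%.

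| Method, 260/130, 94% vs 89% | one-sided 0.025 | Pocock 0.0147 | difference |
|---|---|---|---|
| Normal approximation | 80.2% | 73.6% | 6.6 points |
| Exact enumeration, no continuity correction | 82.3% | 75.7% | 6.6 points |
| Exact enumeration, continuity correction | 76.0% | 68.6% | 7.4 points |

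The last column is also the probability, at the design rates, of a final result that meets one criterion and fails the other. By the same formula, 80% power at the Pocock level would need 151 + 302 = 453 patients.

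**4. A result in the gap.** Take 122/130 (93.8%) on NECT and 226/260 (86.9%) on fexinidazole, without continuity correction:

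- difference −6.9 points, SE 0.0297
- Z = (−0.0692 + 0.13)/0.0297 = 2.05, one-sided p = 0.020
- 95% lower limit −0.0692 − 1.960×0.0297 = −12.7%, which excludes −13%
- 97.06% lower limit −0.0692 − 2.178×0.0297 = −13.4%, which does not

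With a continuity correction of (1/130 + 1/260)/2 = 0.0058, the 95% limit of this result is −13.3% and p = 0.032, so both criteria fail. The gap then lies at other counts; it does not vanish, as the last row of the table shows.

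**5. Error if the 95% interval decided the final analysis.** With Z > 2.178 at the interim or Z > 1.960 at the end, the overall one-sided error by bivariate normal is 3.4% at correlation 0.707 and 3.9% at correlation 0, against 2.5% intended. A binomial simulation at true rates 94% and 81% (looks at 65/130 and 130/260, same endpoint) gives about 3.0% without continuity correction and about 1.8% with it.

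**The case against.** **The 9.8.1 sentence is not a decision rule.** A reader might infer from it that the 95% interval overrides the primary test, so that a borderline trial is formally both positive and negative. The document does not support this. The sentence is confined to benefit-to-risk assessment, and the sentence before it warns against reading too much into a significant test. The Blackwelder test remains the only named primary test. This objection stands. What remains is narrower: the interval given interpretive weight is at a different level from the test.

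**Figure 3 describes power planning.** Its text explains a plotted quantity and does not prescribe how the final analysis will be judged. That is fair as far as it goes. But the text equates the 95% criterion with being significant, and 9.1 uses the same level for what it calls the power of the final analysis. A planning level that differs from the level of the test is itself a discrepancy.

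**Loss of error control does not follow.** A reader might infer that the overall error is inflated. It is inflated only if the 95% interval is used to decide, which no section prescribes. The size also depends on the test version: with a continuity correction the simulated error stays below 2.5%. This stands, so the 3.4% is conditional.

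**The number belongs in the SAP, and a 95% interval beside an adjusted test is common.** Both are true, and the missing Pocock number is no fault in itself. But a SAP that supplied it would still conflict with 9.1 and Figure 3, which state the unadjusted level outright.

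**Conclusion.** The point holds in a limited form. The protocol states two significance levels for the final non-inferiority analysis: the Pocock level in 9.11 (about one-sided 0.0147), and one-sided 0.025 with a 95% interval in 9.1 and Figure 3. Results with Z from 1.960 to 2.178 meet one criterion and fail the other, with a probability of about 6.6% at the design rates (unpooled test, no continuity correction). The stated 80% power applies to the unadjusted level; at the Pocock level it is about 74% (normal) to 76% (exact), both without continuity correction.

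The formal decision stays with the Blackwelder test, so this is an inconsistency to reconcile and not evidence that the primary claim lacks error control. The overall error of about 3.4% would arise only if the 95% interval decided the final analysis after a Pocock interim look; it is a normal approximation and is lower with a continuity-corrected test. The figures rest on the assumed looks at 195 and 390 patients, an overall one-sided 0.025, and treatment of the two visits as one process.

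**What to change.** - **Section 9.11:** state the numeric Pocock level (about one-sided 0.0147 under the assumptions above). Say that non-inferiority is declared only by the primary test at that level, or equivalently only if the two-sided interval of about 97.06% lies above −13%.
- **Section 9.8.1:** report that matching interval for the primary comparison. Label the 95% interval descriptive and say that it cannot override a non-significant primary test.
- **Figure 3:** define significance at the same level.
- **Section 9.1 and the Protocol Summary:** restate the power for 390 patients at 94% versus 89% at that level, about 74% to 76% without continuity correction, and name the version of the test used.

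These are changes of wording and of stated figures; they need no new data. The cost is that the decisive interval becomes about 11% wider (2.178/1.960 = 1.11) and the stated power is less favourable. Restoring 80% at the adjusted level would take about 453 patients, so if the sample size stays at 390 the lower power should be stated openly.

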9.8.2. Sensitivity Analyses

Several sensitivity analyses will be performed to assess the robustness of the result of the primary analysis and to facilitate interpretation. Additional sensitivity analyses may be described in the SAP.

		Population	Efficacy endpoint	Test
Primary anal	Primary analysis		Primary	Primary
	1 st	ITT	Surrogate: actual or predicted outcome for patients with missing data for CSF WBC at 18 months	Primary
	2 nd	Treatment completers	Primary	Primary
Sensitivity analysis	3 rd	Evaluable patients	Primary	Primary
	4 th	Per protocol patients	Primary	Primary
	5 th	ITT	Success or failure, but all patients with no lumbar puncture at 18 months are considered as failures	Primary
	6 th	Study completers with a known CSF WBC at 18 months	Primary (with no imputation)	Primary

The excess failure rate at 18 months based on the K-M estimator can also be considered as a sensitivity analysis.

Analyses exploring the centre effect and interaction between the centre and treatment will be performed primarily to assess the possible generalisability of the size of the effect, i.e. no potential interaction between the centre and treatment, as well as potential bias in estimating the confidence interval of the excess success rate if a significant centre effect is present (see Section 9.3 Handling of Centres; p 60).

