Patients living in an area of armed conflict and who, according to those close to him/her and/or inhabitants of the village, fled the area for a safer region and for whom no post-treatment data are available after several attempts to obtain such information, will not be taken into account in the primary efficacy analysis or in the interim analysis, but will be included in the safety analysis.

Success at 18 months is defined as:

- Patient cured, i.e.
 - o patient alive,
 - o AND no evidence of trypanosomes in any bodily fluid,
 - AND CSF WBC $\leq 20/\mu$ L.

OR

- Patient probably cured, i.e.
 - o no parasites in blood or lymph,
 - AND refusal to undergo lumbar puncture, OR whose CSF sample is haemorrhagic but with no trypanosomes,
 - AND whose clinical status is satisfactory, i.e. with no clinical signs or symptoms, OR whose clinical status is unlikely to be related to HAT.

Failure at 18 months is defined as:

- Patient relapsed, i.e.
 - o evidence of trypanosomes in any bodily fluid,

OR

- Patient probably relapsed, i.e.
 - o Either no evidence of trypanosomes in any bodily fluid,
 - AND CSF WBC > 20/µL,
 - AND whose WBC cannot be explained by a disease other than HAT,
 - o Or no evidence of parasites in the blood or lymph,
 - AND refusal to undergo lumbar puncture, OR whose CSF sample is haemorrhagic but with no trypanosomes,
 - AND who, in the opinion of the Investigator, requires rescue treatment because of marked deterioration in his/her clinical status that is unlikely to be related to a disease other than HAT,
 - Or patient who refuses lumbar puncture at 18 months and in whom the outcome had already been assessed as unfavourable at an earlier time (see Table 1 – Definitions of Early Efficacy Endpoints; p Error! Bookmark not defined.),
 - Or withdrawal from the study due to probable relapse at any time earlier than 18 months (see Table 1 – Definitions of Early Efficacy Endpoints; p Error! Bookmark not defined.)
- Or death, whatever the cause,
- Or lost to follow-up,

Patients living in an area of armed conflict and who, according to those close to him/her and/or inhabitants of the village, fled the area for a safer region and for whom no post-treatment data are available after several attempts to obtain such information, will not be taken into account in the primary efficacy analysis or in the interim analysis, but will be included in the safety analysis.

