12 months	12 months ± 4 weeks	n =195	 Patient alive with no evidence of trypanosomes in any bodily fluid and CSF WBC ≤ 20/µL No evidence of trypanosomes in blood or lymph and refusal to undergo lumbar puncture or whose CSF sample is haemorrhagic but with no trypanosomes and whose clinical status is satisfactory, i.e. with no clinical signs or symptoms, or whose clinical status is unlikely to be related to HAT No lumbar puncture at 12 months, but one at 6 months with CSF WBC ≤ 5/µL 	 No evidence of trypanosomes in any bodily fluid and CSF WBC > 20/µL and whose WBC cannot be explained by a disease other than HAT No evidence of trypanosomes in blood or lymph and refusal to undergo lumbar puncture or whose CSF sample is haemorrhagic but with no trypanosomes and intake of rescue treatment Refusal to undergo lumbar puncture at 12 months and outcome assessed as unfavourable at previous visits Withdrawal from study due to probable relapse at a previous visit No lumbar puncture at 12 months, but one at 6 months with CSF WBC > 5/µL No lumbar puncture at 12 or 6 months 	• Evidence of trypanosomes in any bodily fluid

For statistical purposes, an unfavourable outcome is any situation that does not fulfil the criteria for favourable outcome in Table 1.

Late Efficacy Endpoint (24 months)

The same definitions as those for the primary endpoint will be used. The ideal timing of this visit should be 24 months \pm 4 weeks after EOT.

Surrogate Efficacy Endpoint

The surrogate endpoint is the actual or predicted outcome (if the outcome is missing) at 18 months, based on the outcome at the last visit that took place at 6 months or later, and for which data are available.

The actual outcome, i.e. success or failure, is the same as that defined in the primary endpoint.

The predicted outcome at 18 months is obtained based on logistic models using CSF WBC at baseline, 6 months and/or 12 months, age and sex.

Unlike the primary endpoint, the surrogate endpoint is used to estimate the success rate in the final analysis, i.e. sensitivity analysis of the primary analysis.

In the final analysis, the surrogate endpoint may be much more accurate than the primary endpoint if the predictive value is as good as the results obtained in the set of patients used to construct the models (see Section 9.2 Handling of Missing Values and Lost to Follow-up; p 58).

Safety Endpoints

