5.3. Treatment Allocation

Patients will be randomised at a 2:1 ratio, with two patients in the fexinidazole group for 1 patient in the NECT group.

Each patient who fulfils the inclusion criteria will enter the randomisation process. Treatment will be allocated using a centralised internet-based system in order to avoid bias. After randomisation, the patient will be assigned to one of the two treatment groups, and the number of the treatment pack will be recorded in the patient's file and on the pharmacy log sheet (included in the pharmacy manual).

The patient will be considered to have completed his/her participation in the study once the last protocol-planned visit, i.e. the TOC visit at Month 18, has taken place. The visit at Month 24, at the end of the additional follow-up period, has been planned in order to comply with current recommendations in the National HAT Control Programmes.

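### The 6th sensitivity analysis drops patients already known to have failed before month 18, so it can give false reassurance about robustness

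*Protocol*

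**What the plan says.** Section 9.8.2 of the protocol tabulates six sensitivity analyses meant to test how robust the primary result is.

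- **6th analysis.** The population is "Study completers with a known CSF WBC at 18 months". The endpoint is the primary one without imputation, and the test is the primary test.
- **Completion.** Section 5.3 treats a patient as having completed the study "once the last protocol-planned visit, i.e. the TOC visit at Month 18, has taken place".
- **Failure.** Section 2.2.1 lists "Or death, whatever the cause" among the month-18 failures, together with withdrawal for probable relapse before month 18. Section 9.8.1 adds the use of rescue treatment.
- **General rule.** Section 2.2.2 states that deaths and probable relapses are counted as relapses whatever the analysis. The sentence stands under the early endpoints but is worded generally.
- **1st analysis.** The endpoint cell reads "Surrogate: actual or predicted outcome for patients with missing data for CSF WBC at 18 months". Section 2.2.2 defines the surrogate endpoint as "the actual or predicted outcome (if the outcome is missing) at 18 months" and takes the actual outcome from the primary endpoint.

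**The concern.** Whether a month-18 CSF count exists is decided after randomisation and depends partly on treatment outcome. A patient who dies at month 10 cannot have one. A patient who relapses at month 12 and leaves the study will not have one either. Neither outcome is unknown, because both patients are failures under the protocol's own definition. Counting them as failures is not imputation, so the no-imputation label does not require their removal.

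The 6th analysis nevertheless takes them out of the denominator and out of the failure count. This raises the success rate in both arms. The arm that loses more failures relative to its size gains more. If the lost share of failures is similar in the two arms, that is the arm with more failures, and the difference moves toward zero.

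The stake is interpretation. Section 9.8.1 gives the effect size and its confidence interval precedence over the test result when benefit and risk are weighed. A robustness analysis that selects patients who reached month 18 with a CSF count could appear to confirm a result that it has not tested.

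**Working it through.** **Inputs.** Section 9.1 gives 260 fexinidazole and 130 NECT patients. It also states "The calculations were made for a one-sided type-1 error of 0.025" and "If the expected success rates are 94% with NECT and 89% with fexinidazole". Section 9.8.1 sets the margin at 13 points. The protocol does not give the share e of each arm's failures that are known before month 18 and have no month-18 count. I assume e = 25%, 50% or 75%, equal in both arms, with no other missing data.

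**The plan's own figure.** Section 9.1 says "then the power of the final analysis is 80" per cent.

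- SE = sqrt(0.94×0.06/130 + 0.89×0.11/260) = 0.0285.
- (0.13 − 0.05)/0.0285 − 1.96 = 0.85, so the power is 80.2%. The figure is reproduced.
- Exact binomial enumeration of the unpooled non-inferiority test gives 82.3% at 89% vs 94%. At 81% vs 94%, a true difference equal to the margin, it gives 2.3%.

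**Effect of the selection.** With true success rate s, the retained share of an arm is 1 − e(1 − s), and the success rate among those retained is s/[1 − e(1 − s)]. For e = 50%:

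- NECT: 0.94/0.97 = 96.9%.
- Fexinidazole at 89%: 0.89/0.945 = 94.2%, a difference of −2.7 points.
- Fexinidazole at 81%: 0.81/0.905 = 89.5%, a difference of −7.4 points.

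| e | True 89% vs 94%: expected rates | Difference (points) | True 81% vs 94%: expected rates | Difference (points) | P(analysis supports non-inferiority) at true −13 |
|---|---|---|---|---|---|
| 0 | 89.0 vs 94.0 | −5.0 | 81.0 vs 94.0 | −13.0 | 2.3% |
| 25% | 91.5 vs 95.4 | −3.9 | 85.0 vs 95.4 | −10.4 | 13.5% |
| 50% | 94.2 vs 96.9 | −2.7 | 89.5 vs 96.9 | −7.4 | 60.3% |
| 75% | 97.0 vs 98.4 | −1.4 | 94.5 vs 98.4 | −4.0 | 99.5% |

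The last column is exact enumeration at the expected retained numbers (248/128, 235/126 and 223/124). A simulation of 50,000 trials per scenario gave 13.7%, 61.5% and 99.4%. All use one-sided 0.025. A stricter threshold, such as the Pocock adjustment foreseen in Section 9.11, would lower these probabilities but not the shift in the estimate.

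**Direction.** The planning rates imply 0.11×260 = 28.6, about 29 fexinidazole failures, and 0.06×130 = 7.8, about 8 NECT failures. With all kept, 29/260 vs 8/130 gives −5.0 points. Dropping a few known failures gives the following (lower limit = difference − 1.96×SE):

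| Dropped, fexinidazole / NECT | Remaining failures | Difference (points) | Lower limit |
|---|---|---|---|
| 5 / 0 | 24/255 vs 8/130 | −3.3 | −8.7 |
| 4 / 2 | 25/256 vs 6/128 | −5.1 | −10.2 |
| 3 / 3 | 26/257 vs 5/127 | −6.2 | −11.2 |
| 0 / 5 | 29/260 vs 3/125 | −8.8 | −13.4 |

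The split by arm decides the direction. Losing the same share of failures in each arm shrinks the difference. Losing the same share of patients (4/260 and 2/130, 1.5% each) leaves it almost unchanged. Losing mainly NECT failures works against non-inferiority.

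**The case against.** The best defence of the 6th analysis is that it is openly a completers analysis and only one of six. The 5th analysis bounds it from the other side by counting every patient without a month-18 puncture as a failure. Section 9.8.2 also allows the Kaplan-Meier estimate at 18 months to serve as a sensitivity analysis, and that should keep earlier failures as events. Relapse does not automatically remove a patient either: Section 8.3 lists only withdrawal of consent and study termination as withdrawal grounds, and a rescued patient with a month-18 count stays in as a failure. The share e is assumed throughout.

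Much of this stands. It limits the size of the problem and shows that other analyses retain these failures. It does not make the 6th analysis correct. Deaths before month 18 are excluded in every case, and Section 2.2.1 itself foresees withdrawal for probable relapse. Even if the general rule in Section 2.2.2 is read as confined to the early endpoints, Sections 2.2.1 and 9.8.1 still make these patients known failures.

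A reader might also infer from the 1st-analysis cell that known deaths and relapses are overwritten by model predictions and may become cures. The document does not support that. The protocol summary and Section 2.2.2 use prediction only when the outcome is missing, and the actual outcome follows the primary endpoint. Section 9.2 sets the cut-off on patients whose month-18 outcome is unknown. The models need a 6- or 12-month CSF count, so a death before month 6 could not be predicted at all. What remains is a loosely worded cell.

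**Conclusion.** The point holds for the 6th analysis. As written, it excludes patients whom the protocol defines as failures, and it conflicts with the rule in Section 2.2.2. If half of each arm's failures were lost this way, the expected difference at the planning rates would be −2.7 instead of −5.0 points. At a true −13 points the analysis would support non-inferiority about 60% of the time instead of 2.3%. These figures illustrate an assumed share and equal proportional loss of failures in both arms; they do not forecast what the trial will show.

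Two stronger conclusions should not be drawn. The analysis does not always favour fexinidazole, since the direction depends on how the lost failures split by arm. It also does not inflate the trial's type I error: the conclusion rests on the primary test, and nothing in the protocol lets the 6th analysis replace it. The harm is possible false reassurance about robustness. For the 1st analysis only a wording alignment is needed.

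**What to change.** In the Section 9.8.2 table, redefine the 6th population as patients with a month-18 CSF white cell count plus all patients whose failure (death, confirmed or probable relapse, or rescue treatment) was established before month 18. Exclude only patients whose outcome is unknown. In the 1st-analysis row, replace the trigger of an absent month-18 CSF count with a missing month-18 outcome, so that the cell matches the protocol summary and Section 2.2.2.

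The cost is two table cells and no new data. The 6th-analysis estimate may become slightly less favourable, and the analysis is no longer confined to patients with a month-18 CSF count. Early failures would stay in without a count while successes would still need one, which may lower the success rate somewhat in both arms and should be stated when the result is reported.
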